7.3 Auscultatory Blood Pressure Measurement Procedure

7.3.1 Place the bell of the stethoscope on the brachial artery. Remind subject to refrain from speech and excessive movement during measurement. Two qualified observers, who may be research staff, will listen to the Korotkoff sounds using the ear pieces of the stethoscope. See Figure 9.

[figure not shown]

Figure 9. Auscultatory blood pressure measurement using a stethoscope.

7.3.2 Connect inflation pump to the cuff and inflate to 20-30 mmHg above the systolic pressure, the point at which radial pulse is no longer audible.

7.3.3 Deflate cuff slowly at a rate of approximately 2-3 mmHg/sec. Each observer will listen to Korotkoff sounds and record the systolic and diastolic values independently on a data collection sheet; observers will be blinded to each other's reading and will be provided with their own data collection sheet or will be recording the measurements on independent electronic forms. Observers should avoid parallax errors when reading the pressure gauge by orienting their line of sight directly above the gauge.

7.3.4 A research coordinator will obtain the blood pressure results from each observer's data collection sheet, and will record the values into the paper case report form (CRF). The coordinator will compute the results from the readings and confirm if the paired measurement is valid. A valid measurement is when the observers' blood pressure values are within 4mmHg ($|\text{Observer1 Systolic} - \text{Observer2 Systolic}| \leq 4\text{mmHg}$, and $|\text{Observer1 Diastolic} - \text{Observer2 Diastolic}| \leq 4\text{mmHg}$). If an electronic CRF is being used, difference between the Observer1 and Observer2 readings will be performed by the system.

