7.2 Study Procedure

7.2.1 Ensure the subject is in a relaxed and comfortable position, either seated or lying down, with the arm at heart level and legs uncrossed. Subject should be in the same position for at least 5 minutes prior to blood pressure measurement. During that time, subject demographics and health history may be completed in the CRF.

7.2.2 [REDACTED].

7.2.3 Measure arm circumference and place the appropriate size cuff preferably on the left arm of the subject. The middle of the cuff should be at same level as the heart, see Figure 8. Do not place cuff on an extremity selected for IV infusions or any other intravascular access, e.g. dialysis.

7.2.4 Perform an auscultatory measurement. See section 7.3 for details on the auscultatory measurement procedure (reading R_0 in Figure 7).

7.2.5 Wait at least 60 seconds to allow venous blood flow to normalize.

7.2.6 [REDACTED].

7.2.7 Perform [REDACTED] blood pressure measurement procedure (T_0 in Figure 7).

7.2.8 Wait at least 60 seconds to allow venous blood flow to normalize.

7.2.9 Remove the Masimo cuff and automated blood pressure device and replace with the reference auscultatory cuff and stethoscope.

7.2.10 Perform an auscultatory measurement (R_1 in Figure 7).

7.2.11 Repeat 7.2.5-7.2.10 until at least four valid automated and auscultatory measurement pairs have been performed or eight measurement pairs have been attempted.

- A measurement pair is considered valid if the observer difference criteria in 7.3.4 is satisfied and the automated blood pressure device performs a successful measurement.
- Counting begins with measurement pair T_0-R_1 (e.g. $T_0-R_1, T_1-R_2, T_2-R_3 \dots$ maximum up to T_7-R_8 . See Figure 7).

7.2.12 If less than four paired measurements are obtained after eight paired attempts, subject participation in the study will end.

7.2.13 Be sure to check cuff site health and integrity between measurements.

7.2.14 Disinfect auscultatory blood pressure cuff and allow to air dry, per manufacturer's cleaning directions, after use with each patient.

7.2.15 No treatment decisions will be made based on blood pressure results from study devices.

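### Are the two auscultatory observers left unmasked to the device reading that precedes each reference reading?

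*Combined protocol and SAP*

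**What the plan says.** The reference is auscultation with an aneroid sphygmomanometer and a dual stethoscope (Section 6). Section 7.3.1 provides that "Two qualified observers, who may be research staff, will listen to the Korotkoff sounds". Section 7.3.3 has each observer "record the systolic and diastolic values independently on a data collection sheet; observers will be blinded to each other", meaning to the other's reading, with separate sheets or independent electronic forms, and it warns about reading the dial: "Observers should avoid parallax errors when reading the pressure gauge by orienting their line of sight directly above the gauge".

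Section 7.2 sets the order. An initial auscultatory reading R_0 is taken, then a device reading T_0, then R_1, and so on. "Counting begins with measurement pair T_0-R_1", so each reference reading is paired with the device reading just before it. Step 7.2.8, between the two, reads "Wait at least 60 seconds to allow venous blood flow to normalize". Step 7.2.9 then takes away both the Masimo cuff and the automated device before the reference cuff and stethoscope go on. Step 7.2.11 says "Repeat 7.2.5-7.2.10 until at least four valid automated and auscultatory measurement pairs have been performed", with a ceiling of eight attempts.

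Under 7.3.4 a research coordinator, not the observers, collects the two sheets, enters the values in the CRF and confirms that the observers agree within 4 mmHg on both pressures.

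Steps 7.2.2 and 7.2.6 and part of 7.2.7 are redacted. Section 7.4, the device procedure, appears as a heading only. Figure 7 is not shown, and the text between Sections 3 and 5 is not available.

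**The concern.** The reference is a human judgement: a sound heard and matched by eye to a moving needle. An observer who already knows the device's answer may, without intending to, hear the sounds nearer to it. The order of readings makes this possible in every counted pair. The only masking that 7.3.3 names is between the two observers. Because observers can be research staff, it is easy to picture one of them running the device or seeing the laptop.

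The objective in Section 2 is the mean and SD of the device-reference difference, and Section 8 requires the device to meet two accuracy criteria. A pull towards the device would reduce both statistics and so would always favour the device. The agreement check in 7.3.4 compares the observers with each other, so it cannot detect a shift that they share.

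**Working it through.** **1. What the readable text establishes.** Section 7.3.3 states masking between observers and is silent on the device. Section 7.2.11 puts T before R in each pair. No readable sentence says that observers operate the device, see its display, or hear or record its value. Some readable steps point mildly the other way. The device is removed before each reference reading (7.2.9). Observers record only their own values on separate sheets or forms (7.3.3). A coordinator handles the data (7.3.4). None of these proves masking, since a value could be seen before the device is removed.

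**2. What cannot be read.** The steps around the device measurement (7.2.6, part of 7.2.7, 7.4) are withheld. A rule on hiding the display belongs there at least as naturally as in 7.3.3. Its absence from the public text is therefore no evidence of its absence from the plan.

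**3. What exposure would do, if it occurred.** No figure in the plan depends on this point: the 85 subjects come from the cited standard, and 85 × 4 = 340 pairs. Let T be the device value, R the reference with no pull, and f the fraction of the gap by which both observers move. Then

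R* = R + f(T − R), so T − R* = (1 − f)(T − R).

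Mean and SD are both multiplied by (1 − f). With an assumed mean of 5 mmHg and SD of 8 mmHg:

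- f = 0.1: 0.9 × 5 = 4.5; 0.9 × 8 = 7.2
- f = 0.3: 0.7 × 5 = 3.5; 0.7 × 8 = 5.6

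A simulation of 85 subjects with 4 pairs each, applying the 4 mmHg rule to one pressure, agrees. It assumes an observer reading SD of 1.5 mmHg and a true-pressure SD of 18 mmHg.

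| f | Mean difference | SD | Pairs passing the 4 mmHg rule |
|---|---|---|---|
| 0 | 4.98 | 8.06 | 94.2% |
| 0.1 | 4.51 | 7.27 | 96.3% |
| 0.2 | 3.99 | 6.44 | 98.2% |
| 0.3 | 3.51 | 5.64 | 99.3% |

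The SD at f = 0 is slightly above 8 because observer noise adds to it: √(8² + 1.5²/2) = √65.125 = 8.07.

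**4. Why the 4 mmHg rule is blind to this.** The observer difference also becomes (1 − f) times its original value. A shared pull therefore makes the observers agree more often, and the pass rate rises as the bias grows.

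**5. What the arithmetic does not show.** It gives the direction of a bias given exposure, not that exposure happens. The values of f, the 5 mmHg and the 8 mmHg are all assumed. The accuracy limits are left to the standard and not printed, so the effect on passing cannot be judged. The observers also have their own recent readings in the same subject (R_0, then R_1 and so on) as an anchor, so the extra pull from a device value is unknown.

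**The case for a change.** The best case for the concern is that 7.3 is the observers' own procedure and its numbered steps can be read in full. The sponsor chose to write masking into 7.3.3 and named only one target. Someone on site must know whether each device reading succeeded, because validity and the stopping count depend on it (7.2.11). Device readings are among the CRF contents in Section 10.3, and the data-acquisition laptop is study equipment. Section 8 defers sample size and analysis to the ISO standard, not observer conduct. Section 3 says only that the design is based on that standard, which tells site staff nothing about screens. A clarifying sentence would cost little.

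Much of this stands. The readable text is silent, exposure is conceivable, any resulting bias would favour the device, and the agreement rule would miss it. What does not stand is the step from silence to observers being unmasked. Knowing that a reading succeeded is not knowing its value, and Section 10.3 does not say that observers enter or see device readings. Nor is it clear that masking would be free: barring observers from operating the device might need another person, and the documents do not say who operates it.

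**Conclusion.** The concern does not support a change to the plan. It is right about the wording of 7.3.3, the order of the readings and the blind spot of the 4 mmHg rule. It fails on its central claim, because nothing shows that observers learn the device value, and the steps most likely to govern this are withheld from the public text. What remains is a gap of detail in the readable document, of a kind that a site running a two-observer comparison would ordinarily fill by keeping the device value from the observers. Anyone holding the unredacted protocol can settle it by reading 7.2.6, 7.2.7 and 7.4.

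On size: if exposure did occur, the mean and SD would each shrink by the fraction f, for example from 5 and 8 mmHg to between 4.5 and 3.5 and between 7.2 and 5.6 for f of 10% to 30%. Those inputs are assumptions, and the documents give no basis for choosing f or for saying that it differs from zero. The conclusion rests on treating withheld text as unknown rather than missing. If the full protocol proved equally silent, the point would deserve a fresh look.

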7.4 Automated Blood Pressure Measurement Procedure

8 SAMPLE SIZE CALCULATION AND STATISTICAL ANALYSIS

The sample size requirements and statistical analysis are completely defined by the international standard for non-invasive sphygmomanometers, ISO 81060-2:2018, 3rd Edition. A minimum of 85 subjects are required, and the predicted blood pressure values must pass the two accuracy criterions defined in the standard. Population distributions are clearly defined and will be followed for blood pressure ranges, gender, and arm circumference across each cuff size.

9 SAFETY AND ADVERSE EVENTS

9.1 Definitions

The definitions for adverse event, adverse device effect, serious adverse event, serious adverse device effect, and unanticipated adverse device effect are provided below (ISO 14155:2011, 21 CFR 812.3(s)).

- **Adverse Event (AE):** an adverse event is any untoward medical occurrence in a subject which need not be related to the device under investigation.
- **Adverse Device Effect (ADE):** an adverse device effect is any untoward or unintended response to a medical device which may result from insufficiencies in the instructions for use or deployment of the device, or from use error.
- **Serious Adverse Event (SAE):** a serious adverse event is an adverse event that results in death, inpatient hospitalization, severe or permanent disability, a life threatening illness or injury, fetal distress, fetal death, a congenital abnormality, a birth defect, or medical or surgical intervention to prevent permanent impairment to body or structure.
- **Serious Adverse Device Effect (SADE):** a serious adverse device effect is an adverse device effect that results in death, inpatient hospitalization, severe or permanent disability or is life threatening.
- **Unanticipated Adverse Device Effect (UADE):** any serious adverse effect on health or safety or any life threatening problem or death cause by or associated with, a device, if the effect, problem, or death was not previously identified in nature, severity or degree of incidence in the investigational plan, or application (including a supplementary plan or application) or any other unanticipated serious problem associated with a device that related to the rights, safety or welfare of subjects. Refer to the Device Risk Analysis and Risk Assessment section in the investigator's brochure for details on anticipated adverse device effects.

9.2 Anticipated Adverse Events:

- Subject may feel slight discomfort temporarily during blood pressure cuff inflation.
- Bruising may be possible in some subjects.
- Subject may develop possible ischemia, purpura, and/or neuropathy at the site of the cuff or at the extremity. Cuff site will be inspected by research staff throughout measurements for any signs of adverse events. Subject participation will be stopped if adverse events are observed.

9.3 Adverse Event Reporting:

- All Adverse Events, both Anticipated and Unanticipated, must be recorded in the within the CRF and in the Adverse Event Report Form.
- All Adverse Events must be promptly reported to the Sponsor.
- All Unanticipated Adverse Device Effects will be also reported to both the Sponsor and the IRB.
- Both Serious Adverse Events and Unanticipated Adverse Device Effects must be reported to the Sponsor within 48 hours. All other Adverse Events should be reported to the Sponsor within 5 business days.
- All Serious Adverse Events will be also reported to the IRB per IRB reporting requirements. These reports may include, but will not be limited to: date of onset; brief description of the events; their treatment; whether they resulted in death, inpatient hospitalization, severe or permanent disability or were life threatening; their relationship to the study device; and resolution.

9.4 Deviations from the study protocol

Deviations from the protocol must receive both Sponsor and the investigator's IRB approval before they are initiated. Any protocol deviations initiated without Sponsor and the investigator's IRB approval that may affect the scientific soundness of the study, or affect the rights, safety, or welfare of study subjects, must be reported to the Sponsor and to the investigator's IRB as soon as a possible, but no later than 5 working days of the protocol deviation.

9.5 Withdrawal of IRB approval

An investigator shall report to the sponsor a withdrawal of approval by the investigator's reviewing IRB as soon as possible, but no later than 5 working days of the IRB notification of withdrawal of approval.

10 DATA MANAGEMENT

10.1 Data Management and Confidentiality

All documents associated with this protocol will be kept in the locked office of the PI or on password protected computers. All data will be de-identified before any statistical analysis. Only de-identified data will be shared with Masimo for research purposes stated in this protocol. Data collected by data capture software and data entered in case report form will be shared with Masimo via a secure, password protected server that only study staff and Masimo study team members will have access to. Data will be retained for a minimum to 2 years following completion of the final analysis.

10.2 Source Documents

Source data is all information, original records of clinical findings, observations, or other activities in a clinical trial necessary for the reconstruction and evaluation of the trial. Source data are contained in source documents. Examples of these original documents and data records include: hospital records, clinical and office charts, laboratory notes, memoranda, recorded data from automated instruments, and copies or transcriptions certified after verification as being accurate and complete.

10.3 Case Report Forms

The Sponsor shall provide a paper Case Report Form (CRF) template to the site. The site shall capture study data in the CRFs for each subject enrolled. The CRFs will be completed and signed by principal investigator. This also applies to those subjects who fail to complete the study. If a subject withdraws from the study, the reason must be noted on the CRF. Case report forms are to be completed on an ongoing basis. CRF entries and corrections will only be performed by study site staff, authorized by the investigator. Entries and corrections to the CRF will be made following Good Documentation Practices.

The CRF will include the following information, including but not limited to: inclusion / exclusion criteria, whether patient consent obtained before start of study, demographic information, device readings, and if occurrence of any adverse event, protocol deviation, and device deficiencies, etc. The CRF will be signed by the PI and forwarded to Masimo.

CRF entries will be checked by study monitor and any errors or inconsistencies will be queried to the site on an ongoing basis. Query resolution will be assessed and confirmed by study monitor during site visit.

10.4 Data Transfer and Storage

The information will be stored in a password protected electronic database at the study site. Device data along with an electronic copy of the CRF will periodically be securely uploaded to sponsor via secure portal. Only authorized sponsor personnel will have access to the transferred data, and will move it to a secure and backed-up drive at Masimo. Device data and electronic copy of CRFs will be checked for completeness. If there are inconsistent or missing data points, a data query log will be generated and submitted to the site for correction. If the investigator is to correct the CRF, the PI shall follow GDP practices to strike through old entry, add in new entry, and initial and date it, and resend the updated corrected CRF copy to Masimo. Once all queries have been resolved, Masimo engineers are notified that data is ready for analysis. To ensure data integrity, Masimo engineers will only have read access to data, therefore are unable to unintentionally tamper with the original data files. Raw and processed physiological data will be analyzed by Masimo Engineering team.

10.5 Record Retention

Study data will be retained for the necessary period of time as required by the institution's regulations. Study records shall be retained for a minimum of two years after study closure. The Institution's own retention policies and regulations may apply in addition to the minimal requirement.

11 MONITORING PLAN

11.1 As the sponsor of this clinical investigation, Masimo Corporation is required by 21 CFR Part 812, of the Food and Drug Administration regulations to monitor and oversee the progress of the investigation. The monitor(s) assigned by Masimo Corporation to this task will be trained on departmental SOPs on conduct and monitoring of sponsored studies.

11.2 In accordance with good clinical practices guidelines, there will be at least three scheduled monitoring visits to ensure overall regulatory compliance of the study:

- An initiation visit, prior to any subject enrollment to confirm site readiness, and to document training on the study protocol and procedures, and use of equipment.
- At least one monitoring visit during initial enrollment, and/or at least one visit 4-6 weeks after data collection is complete.
- A final close out visit after the last patient had finished the study.
- NOTE DURING COVID-19 PANDEMIC: on-site monitoring visits will be highly unlikely. Monitoring activities may be modified or postponed until such a time that restrictions prohibiting travel and hospital access are lifted.

11.3 The monitor will contact and visit the investigator and will be allowed, on request, to have access to all source documents needed to verify the entries in the CRFs and other GCP-related documents (IRB approvals, IRB correspondences, and ICFs) provided that subject confidentiality is maintained in agreement with HIPAA regulations.

11.4 It will be the monitor's responsibility to inspect the CRFs at regular intervals throughout the study, to verify the adherence to the CIP and the completeness, consistency and accuracy of the data being entered on them.

11.5 During each visit, the monitor will also verify presence of informed consent, adherence to the inclusion/exclusion criteria, and documentation of SAEs/SADEs and protocol deviations/violations, and check CRF against source documentation.

11.6 After each visit, the monitor will provide a monitoring follow-up letter to the investigator within 4 weeks of visit completion. The monitoring follow-up letter will detail findings and open action items observed during the visit. It is the responsibility of the Principal Investigator and Study Coordinator(s) to respond to the findings of the monitoring follow-up letter, and complete any open action items as soon as possible but no later than 60 days of receiving the monitoring report. Any open action items not completed within the time allowed may be sufficient grounds for study site suspension or termination; it will be up to the sponsor to determine whether any incomplete action items are sufficient grounds for suspension or termination. See Section 13 for details on suspension and termination.

11.7 Depending on the quality of the data and/or changes to factors affecting patient safety, additional monitoring visits may be necessary according at the sponsor's discretion.

12 VULNERABLE POPULATIONS

12.1 Definition

12.1.1 Vulnerable population are research participants, such as children, prisoners, pregnant women, handicapped, or mentally disable persons, or economically or educationally disadvantaged persons, who are likely to be vulnerable to coercion and undue influence. This study may enroll economically or educationally disadvantaged subjects.

The federal regulations that govern the protection of human subjects require additional protection for the vulnerable population.

12.2 Protection of vulnerable subjects

- Reasonable compensation will be provided for economically disadvantaged subjects to eliminate possibility of undue influence due to financial incentive.
- Educationally disadvantaged subjects will be provided ample time to ask questions and comprehend information.
- Medical care will be provided to these subjects after the clinical investigation has been completed if they are injured as a direct result of participating in this research study. The cost of treatment for any research related injury will be covered by Masimo.

12.3 Responsible Parties

- The EC/IRB will review research with vulnerable populations and evaluate consent, level of risk, coercion, and the reason for choosing this particular subject population. The EC/IRB will be responsible for determining what practices will include continuing review for compliance while monitoring these studies.
- The Investigator holds the ultimate responsibility for protecting the rights, safety, and welfare of research subjects by ensuring that all regulations and proper documentation of consent is handled in a compliant and timely manner.

